5.3 Exclusion Criteria

1. Patients who have had hip arthroplasty or conditions such as, hip osteoarthritis, iliopsoas bursitis, reactive arthritis, rheumatoid arthritis, psoriatic arthritis, ankylosing spondylitis, or arthritis associated with inflammatory bowel disease
2. History of local infection around the bursa;
3. Lack of pain relief with intra-bursal treatments containing an anesthetic
4. Intra-bursal treatment of any bursa with any of the following agents within three (3) months of screening: any corticosteroid preparation (investigational or marketed, including FX006); and/or six (6) months for any biologic agent (e.g., platelet rich plasma (PRP) injection, stem cells, prolotherapy, amniotic fluid injection; investigational or marketed).
5. Parenteral or oral corticosteroids (investigational or marketed) within 3 months of screening; Inhaled, intranasal or topical corticosteroids (investigational or marketed) within 2 weeks of screening;
6. Females who are pregnant or nursing or plan to become pregnant during the study; women who plan to conceive during the study.

6 CONCURRENT MEDICATIONS

All subjects should be maintained on the same medications throughout the entire study period, as medically feasible, with no introduction of new chronic therapies medication.

6.1 Allowed Medications and Treatments

Standard therapy for hip pain is allowed, except for treatments noted in the exclusion criteria described above and as noted in the prohibited medications section below.

6.2 Prohibited Medications and Treatments

The following medications are prohibited during the study:

- Intra-bursal treatment of any bursa with any of the following agents within six (6) months of screening: any corticosteroid preparation (investigational or marketed, including FX006), any biologic agent (e.g., platelet rich plasma (PRP) injection, stem cells, prolotherapy, amniotic fluid injection; investigational or marketed).
- Parenteral or oral corticosteroids (investigational or marketed) within 3 months of screening
- Inhaled, intranasal or topical corticosteroids (investigational or marketed) within 2 weeks of screening.

7.1 Treatment Plan

The patient will make a one-time visit to the outpatient radiology department at Memorial Hermann Hospital at the Texas Medical Center, and will be expected to stay for a maximum of 2 hours. Each patient will be consented for the procedure and a baseline assessment using the NPRS and PGIC measures will be made.

24 patients will be injected with the 5ml of FX006. This injection may be followed with up to 3ml of ropivacaine (depending on the capacity of the bursa), under ultrasound guidance. The data collected from the patient and subsequent follow-up will be maintained by the clinical team throughout the 12 weeks of the subject participation.

7.1.1 Formulation of Test Product

FX006 is an extended-release formulation of Triamcinolone Acetonide (TA), developed by Flexion Therapeutics, for the management of pain of osteoarthritis. FX006 contains TA, formulated in 75:25 polylactic-co-glycolic acid (PLGA) microspheres with a nominal drug load of 25% and is provided as a sterile white to off-white powder for reconstitution. The drug product is reconstituted with diluent containing an isotonic, sterile aqueous solution of sodium chloride, carboxymethylcellulose sodium and polysorbate-80 to form a suspension prior to Intra-Articular injection.

7.1.2 Packaging and Labeling

Study drug is supplied in a package kit containing one (1) vial of FX006, one (1) vial Diluent, and a vial adapter.

The FX006 and diluent vials will be labeled with the respective unique lot numbers within the packaged kit, which will be affixed with its own label and kit number.

7.2 Supply of Study Drug at the Site

Flexion Therapeutics, Inc. will ship Study Drug to the investigational sites. The initial FX006 study drug shipment will be made after site activation (i.e., all required regulatory documentation has been received by Flexion Therapeutics, Inc. and a contract has been executed). Subsequent study drug shipments will be made after site request for resupply. All drugs will be stored in the Investigational Drug Service (IDS) pharmacy of the Memorial Hermann Hospital at the Texas Medical Center, prior to use, in a monitored refrigerator, and dispensed as prescribed.

7.2.1 Dosage/Dosage Regimen

FX006 will be reconstituted according to the instructions for use, using aseptic techniques. It will be administered at the standard dosage of 32 mg and injected into the hip bursa using ultrasound guidance. This injection may be followed with up to 3 mL of ropivacaine (the actual volume of ropivacaine injected will be up to the discretion of the radiologist and will be based on the capacity of the bursa). Medication will be administered once per subject.

7.2.2 Dispensing

FX006 will be dispensed by the IDS pharmacy to the research nurse or other study personnel after the prescription is submitted to the pharmacy. Research personnel that are receiving FX006 will sign the chain of custody log in the pharmacy. FX006 will be dispensed in packaging supplied by manufacturer.

7.2.3 Administration Instructions

FX006 will be administered in standard dosage of 32 mg injected into hip bursa using ultrasound guidance using aseptic technique. This injection may be followed with up to 3 mL of ropivacaine (depending on the capacity of the bursa). Medication will be administered once per subject.

7.2.4 Storage

Study drug will be stored by the IDS pharmacy in a designated, monitored refrigerator, 2 to 8°C. If the temperature of study drug storage in the clinic/pharmacy exceeds or falls below this range, this may be reported to Flexion Therapeutics, Inc., for guidance on disposition.

7.3 Study Drug Accountability

An accurate and current accounting of the dispensing study drug for each subject will be maintained on an ongoing basis by a member of the study site staff. The study drug dispensed will be recorded on the Investigational Drug Accountability Record. Used study drug vials will be disposed of appropriately according to the site protocols.

8 STUDY PROCEDURES AND GUIDELINES

A Schedule of Events representing the required testing procedures to be performed for the duration of the study is detailed in Appendix 1.

Prior to conducting any study-related activities, written informed consent and the Health Insurance Portability and Accountability Act (HIPAA) authorization must be signed and dated by the subject.

8.1 Clinical Assessments

8.1.1 Concomitant Medications

All concomitant medication and concurrent therapies will be documented at screening and during each follow-up telephone call and upon study discontinuation. Dose, route, unit frequency of administration, and indication for administration and dates of medication will be captured.

8.1.2 Demographics

Demographic information (date of birth and gender) will be recorded at screening.

8.1.3 Medical History

Relevant medical history, including history of current disease, other pertinent history, and information regarding underlying diseases will be recorded at screening.

8.1.4 Physical Examination

A focused physical examination will be performed by either the investigator or a sub-investigator who is a physician at screening.

8.1.5 Vital Signs

Measurement of body temperature, blood pressure, pulse and respiration will be performed after the subject has rested for 5 minutes on the treatment date.

8.1.6 Other Clinical Procedures

Subjects will be asked about their Numeric Pain Rating System (NPRS) on a 1 to 10 scale, and will be asked about their Patient Global Impression of Change (PGIC) scores during each follow-up telephone call.

8.1.7 Adverse Events

Information regarding occurrence of adverse events will be captured throughout the study. Duration (start and stop dates and times), severity/grade, outcome, treatment and relation to the study drug will be recorded on the case report form (CRF).

9 ADVERSE EXPERIENCE REPORTING AND DOCUMENTATION

9.1 Collection

Adverse events will be collected from the time of medication administration until completion of the follow-up telephone calls at week 12 or until subject participation in study ends.

The Investigator or other medical trained personnel will probe, via discussion with the subject, for the occurrence of Adverse Events during each subject contact and record the information in the source documents. Adverse events will be recorded in the patient CRF. Adverse events will be described by duration (start and stop dates and times), outcome, and treatment. The Investigator, or other medical trained personnel will also assess the seriousness and severity of the event, and relationship of the event to study drug according to the definitions below. If unrelated to study drug, the more likely cause of the event will also be assessed and recorded.

9.2 Definitions

Adverse Event (AE): Any untoward medical occurrence in a clinical investigation of a patient administered a pharmaceutical product and that does not necessarily have a causal relationship with the treatment. An AE is therefore any unfavorable and unintended sign (including an abnormal laboratory finding), symptom or disease temporally associated with the administration of an investigational product, whether or not related to that investigational product. An unexpected AE is one of a type not identified in nature, severity, or frequency in the current Investigator's Brochure or of greater severity or frequency than expected based on the information in the Investigator's Brochure.

Serious Adverse Event (SAE): An SAE is any untoward medical occurrence that at any dose:

- Results in death,
- Is life-threatening, ("Life-threatening" refers to an event in which the patient was at substantial risk of death at the time of the event; it does not refer to an event which hypothetically might have caused death if it were more severe.)
- Requires inpatient hospitalization or prolongation of existing hospitalization,
 - Note: Adverse events requiring hospitalizations that are less than 24 hours in duration generally do not meet this criterion. A scheduled hospitalization for an elective procedure or a pre-existing condition that has not worsened during participation in the

study does not meet this criterion.

- Results in permanent or significant disability/incapacity; a substantial disruption of the patient's ability to carry out normal life functions.
- Is a congenital anomaly/birth defect.
- Is an important medical event: event that may not be immediately life-threatening or result in death or hospitalization but may jeopardize the patient or may require intervention to prevent one of the outcomes listed in the definition above.

Severity: the intensity of the adverse event. This is not the same as "serious," which is based on patient/event outcome or action criteria usually associated with events that pose a threat to a patient's life or functioning. The severity of AEs will be assessed according to the following definitions:

Table 1: AE Severity Grading

Severity	Description
Mild	The AE is noticeable to the patient and/or the Investigator, but does not interfere with routine activity.
Moderate	The AE interferes with routine activity, but responds to symptomatic therapy or rest.
Severe	The AE significantly limits the patient's ability to perform routine activities despite symptomatic therapy

Causal Relationship: A medically-qualified Investigator must assess the relationship of any AE (including SAEs) to the use of the investigational product, as related or not related, based on clinical judgment and using all available information. Possible causes of the AE should be considered, including the disease under treatment, pre-existing conditions, concomitant use of other drugs, and presence of environmental or genetic factors, the temporal association between drug exposure and onset of the AE, and whether the manifestations of the AE are consistent with known actions or toxicity of the investigational product. The causal relationship between the study medication and the AE will be assessed using one of the following categories:

Causal relationship	Description
Not Related	An AE is not associated with study medication if: 
○ Temporal relationship is lacking (e.g., the event did not occur within a reasonable time frame following administration of the study medication); or○ Other causative factors more likely explain the event (e.g., a pre-existing condition, other concomitant treatments).

Related	
An AE is attributed to the study medication if:
 
 ○ There is a positive temporal relationship (e.g., the event occurred within a reasonable time frame following administration of study medication); and ○ The AE is more likely explained by the investigational product than by another cause (i.e., the AE shows a pattern consistent with previous knowledge of the investigational product or the class of the investigational product).
----------------	--

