1 BACKGROUND/RATIONALE

Zilretta is approved for intra-articular injection into the knee joint for treatment of osteoarthritis (1). There are ongoing studies for intra-articular injection into the other large joints including the shoulder and hip joints (2). To our knowledge there has been no prior study to prove efficacy of injection of the extended release steroid into the bursa. The bursae surrounding the hip joint including the iliopsoas and the greater trochanteric bursa are some of the larger bursae in the body. Conventional treatment for inflammation of these bursae is injection of corticosteroids (3). We believe that a long acting corticosteroid, if efficacious, can have a great impact. There is a significant population of patients suffering from chronic bursal pain, who might benefit. At our institution, bursal injection of the steroid in the region of hips is one of the most common locations, second only to joint injections. To our understanding, the bursa surrounding the hip are deep enough to avoid side effects associated with subcutaneous injection of steroid. The current proposal is a pilot study.

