9.4 Reporting to the US FDA

All serious adverse events which are considered causally related to Zilretta must be assessed for whether it is expected per the Investigators Brochure. An unexpected event means that it is not described within the reference safety information (the Zilretta IB) as associated with Zilretta.

If an event is assessed as serious, related to Zilretta, and unexpected, it must be reported to the FDA according to 21CFR312.32.

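### Section 9.2 ties relatedness to previous knowledge and leaves equally explained events without a category, so a serious, wholly new reaction can miss the FDA route in 9.4

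*Combined protocol and SAP*

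**What the plan says.** Section 9.2 (Definitions, Causal Relationship) allows two categories.

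- **Related** needs two conditions together. The first is timing: "There is a positive temporal relationship (e.g., the event occurred within a reasonable time frame following administration of study medication); and". The second is "The AE is more likely explained by the investigational product than by another cause (i.e., the AE shows a pattern consistent with previous knowledge". The parenthesis goes on to accept a pattern "consistent with previous knowledge of the investigational product or the class of the investigational product".
- **Not Related** needs either of two conditions: the timing does not fit, or "Other causative factors more likely explain the event (e.g., a pre-existing condition, other concomitant treatments").

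The paragraph that introduces these categories rests the assessment on clinical judgment over all the information. It lists fit with the product's known actions or toxicity as one consideration among several.

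Section 9.4 states: "If an event is assessed as serious, related to Zilretta, and unexpected, it must be reported to the FDA". It asks whether a serious event is expected only after that event has been judged causally related, and it defines unexpected as not described in the Zilretta brochure. The adverse-event definition in 9.2 is wider: greater severity or frequency than the brochure states also makes an event unexpected.

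On who decides, 9.1 says: "The Investigator, or other medical trained personnel will also assess the seriousness and severity of the event, and relationship of the event to study drug". Section 9.2 says: "A medically-qualified Investigator must assess the relationship of any AE (including SAEs) to the use of the investigational product".

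Section 1 says that, to the authors' knowledge, "there has been no prior study to prove efficacy of injection of the extended release steroid into the bursa".

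**The concern.** The abbreviation i.e. makes the known pattern the meaning of the second condition for Related, not an example of it. The FDA rule then asks for an event that is both related and unexpected. For a reaction with no precedent in the product or its class, the two tests pull against each other: what makes the event unexpected also keeps it from being Related. This matters most when a marketed product is put into a new site, which is the purpose of this pilot.

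The second problem is a gap. Each category asks for one explanation to be more likely than the other, so a tie has no home although one of two labels must be chosen. Ties are foreseeable here. Up to 3 mL of ropivacaine may follow FX006 into the same bursa (7.1, 7.2.1), and the bursa is already diseased.

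At stake are a consistent related/not-related label on the CRF (8.1.7) and the FDA report for a serious, new reaction.

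**Working it through.** The plan gives no figure on this point, so the check is one of logic. Take events whose timing fits the injection. Cross which explanation is more likely (three levels) with what was known beforehand (four levels): 3 × 4 = 12 cases. Apply 9.2 literally.

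| More likely explanation | In the brochure | Class effect, not in the brochure | In the brochure, but more severe than stated | New to product and class |
|---|---|---|---|---|
| Product | Related, expected | Related, unexpected | Related, unexpected | No category |
| Equal | No category | No category | No category | No category |
| Another cause | Not Related | Not Related | Not Related | Not Related |

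1. **Cases with no category, literal reading:** 4 ties + 1 new reaction more likely due to the product = 5 of 12.
2. **Cases with no category if the introduction's appeal to clinical judgment overrides the parenthesis:** the new reaction becomes Related, leaving the 4 ties = 4 of 12.
3. **Cases both related and unexpected, which 9.4 sends to the FDA if serious:** literally 2 of 12 (the class effect and the more severe event). On the judgment reading, 2 + 1 = 3 of 12. The more severe event counts only under the wider definition of unexpected in 9.2. Under 9.4's own definition the counts are 1 and 2.
4. **Unexpected cases that 9.4 does not reach because they have no category:** literally, 3 ties outside the brochure's description + 1 new reaction = 4 of 12. On the judgment reading, 3 of 12.

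Next, set the other safety provisions against the same 12 cases.

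- **Recording:** 9.2 defines an adverse event irrespective of relationship, and 9.1 puts adverse events on the CRF without a causality filter.
- **Summary:** section 12 reports the number and percentage of patients with adverse events within 12 weeks, not limited to related events.
- **Serious events to the IRB:** within 7 days (9.3), whatever the causality (14.2).
- **Serious events to the drug supplier:** all of them, within 3 calendar days (9.3). Section 14.5 also sends any adverse event to the supplier.

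All 12 cases pass through these provisions under both readings. Only 9.4 depends on the label.

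Finally, the assessor. Section 9.1 allows either the Investigator or other trained staff to judge relationship. Section 9.2 makes it a duty of a medically-qualified Investigator. Section 9.1 refers forward to the definitions that follow it, but that does not say which rule governs.

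**The case against.** The strongest defence is that the parenthesis should not be read alone. The introduction to the same part of 9.2 calls for clinical judgment and treats known toxicity as one factor. A sensible investigator who thinks the drug the likelier cause of a new reaction would call it Related and report it. That softens the conflict but does not remove it: the introduction and the category table say different things, and the table is what gets applied. It also does nothing for ties.

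Several stronger readings are tempting, and the documents do not support them.

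- **That a new reaction would go uncounted or wholly unreported.** Recording, the planned summary, and serious-event reporting to the IRB and the supplier all ignore causality.
- **That the rate of related events would be biased downward.** No such rate is specified. Relationship is recorded on the CRF, and section 12 promises descriptive statistics for the clinical variables collected, so the label may be tabulated, but no analysis rests on it.
- **That new events are pushed into Not Related.** A well-timed new event with no better explanation fails that definition too. The text leaves it unclassified. Section 9.1 also requires the likelier cause to be recorded for an unrelated event, which works against Not Related as a default.
- **That almost nothing can be both related and unexpected.** Class effects absent from the brochure can be, and so can known events of greater severity or frequency under 9.2.
- **That there is no safety experience with the route.** Section 1 speaks only of studies proving efficacy.
- **That 24 patients make the loss of one case decisive.** The chance of seeing an event in 24 patients is the same under any causality wording, and a mislabelled case stays in the adverse-event record.

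**Conclusion.** The point holds within narrow limits. Read literally, 9.2 and 9.4 together leave a serious reaction that is new to both product and class outside FDA reporting. Ties have no category on either reading, and 9.1 and 9.2 conflict on who assigns relationship. The affected cases are 5 of 12 (literal) or 4 of 12 (judgment) without a category, of which 4 or 3 are unexpected and so would matter to 9.4 if serious.

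These counts assume that timing fits, that the four knowledge levels cover the possibilities, and that the wider definition of unexpected in 9.2 applies. Under 9.4's own definition, the 4 and 3 become 3 and 2. They are not probabilities, and the documents give no event rates from which to derive any. No efficacy result, adverse-event count, or IRB or supplier report is affected. The defect should still be corrected, because it touches a regulatory report and the correction is short.

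**What to change.** Make three wording changes.

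1. **9.2, Related:** delete the parenthesis or change i.e. to e.g., so that fit with previous knowledge supports the judgment but is not required. This agrees with the section's own introduction.
2. **9.2, categories:** state that any adverse event not meeting the Not Related definition is classed as Related.
3. **9.1:** reconcile with 9.2 so that other trained staff may collect events, but the medically-qualified Investigator assigns relationship.

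The first two edits are both needed. The first alone leaves the ties open, and the second alone still contradicts the literal definition of Related for a new reaction. With both, the 12 cases divide into 4 + 4 = 8 Related and 4 Not Related, with none unclassified. The related and unexpected cases become 3 + 3 = 6 of 12, against 2 on the literal reading now.

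The cost is a few sentences in an amendment, a few more events labelled related, and possibly an extra FDA report. Treatment, assessments and sample size do not change.
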